Regarding research risks, participants may experience fatigue and/or boredom while completing the telephone/online assessments, EMA surveys, and/or the treatment sessions. Some participants may also experience mild anxiety, frustration, and/or stress while answering sensitive questions about depression, pain, and mood. As a result of answering questions about pain, some participants may focus more on their pain, which may lead to a temporary increase in pain intensity. Participants will be told that such phenomena associated with close self-monitoring are a part of the treatment approaches we are offering, and will be addressed as part of the interventions.

E3b. Stress / Discomfort Caused by Treatments

Our research team has had a great deal of experience with each of the treatments to be examined in this study, and each has minimal risks. The three types of treatment involve discussions about pain and related topics in a group setting that may make some individuals feel uncomfortable. Some participants may also experience mild anxiety, frustration, and/or

stress during the course of treatment should any topics or activities prove difficult for them. Some individuals learning cognitive restructuring of thoughts and beliefs or practicing mindfulness meditation may remember past experiences that are uncomfortable and/or cause distress, even after the session has ended. Regarding the mindfulness meditation training, some individuals may find the state of focused awareness uncomfortable, or may experience mild disorientation or grogginess during or after the session has ended due to the occasionally relaxing nature of this practice. Regarding the activation skills intervention, although clinicians will instruct participants engage only in safe and personally appropriate activities, there is a risk that participants may experience physical strain or injury when conducting activities with a physical component.

Should any participants experience these discomforts, the intervention leaders are clinicians with the expertise and clinical privileges needed to address these in appropriate clinical fashion in real time. Study investigators (Drs. [name], [name], and [name]) are also available on site for additional consultation or support if needed. There is little chance of physical injury from the treatment procedures described above.

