The goal of this protocol is to ensure that reasonable steps are consistently taken by study clinicians and investigators to protect participant safety and welfare. The study clinicians will be credentialed and privileged providers at the UW or Masters-level or post-doctoral level clinicians under the supervision of a credentialed and privileged UW provider. Additionally, both [name] and [name] are credentialed, privileged, and licensed providers at the UW. Should there be any indication of risk for self-directed violence that arise during interactions with study staff, the study clinicians/investigators will follow the same specific procedures and policies that psychologists who are clinicians at UW follow for assessing and managing risk.

In instances where the clinician is concerned about safety/suicide risk in a study participant (i.e., if they state or allude to thoughts or plans of self-directed violence, mention recent self-directed violent behavior or behavior preparatory to self-directed violence during a study intervention session), or in instances where a study clinician/investigator is contacted by a research staff member and asked to follow-up with a participant, the study clinicians/investigators will follow the same risk assessment and prevention protocol that is required of UW licensed psychologists.

F. Data Safety Monitoring

F1. Adverse Event & Unanticipated Problems Definitions

F1a. Adverse Event (AE)

An adverse event (AE) is any untoward medical occurrence in a participant during participation in the clinical study or with use of the experimental agent being studied. An adverse finding can include a sign, symptom, abnormal assessment (laboratory test value, vital signs, electrocardiogram finding, etc.), or any combination of these regardless of relationship to participation in the study. Staff will document any occurrence that meets this definition, is a new symptom/condition for the participant, and results in either self-treatment or treatment by a health care provider.

F1b. Unanticipated Problems (UP)

The Office for Human Research Protections (OHRP) considers unanticipated problems involving risks to participants or others to include, in general, any incident, experience, or outcome that meets all of the following criteria:

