F2c. Severity of Event

The following scale will be used to grade adverse events:

1. Mild: no intervention required; no impact on activities of daily living (ADL)
2. Moderate: minimal, local, or non-invasive intervention indicated; moderate impact on ADL
3. Severe: significant symptoms requiring invasive intervention; participant seeks medical attention, needs major assistance with ADL
4. Life-threatening: the event is potentially fatal

F3. Reporting Procedures

F3a. Regulatory Event Documentation

All regulatory events, incidents, or problems involving risks to participants, including AEs, SAEs, and Unanticipated Problems (UP), will be documented in the REDCap electronic database that houses all study data. All regulatory events will share a common electronic form template. Two separate copies of the same form will exist, (1) one for events involving information that could unblind staff to a participant's treatment allocation, and (2) another for events without details that could unblind staff to a participant's treatment allocation. Only unblinded staff will have access to the form that outlines events with details that could unblind staff to a participant's treatment intervention. The form will be filled out for every regulatory event. A study clinician will review all events that are designated AEs or SAEs to assess severity and relationship to study procedures.

The Regulatory Event form will assess the following information for all three event types (AE, SAE, and UP):

- A brief description of the incident/problem.
- Dates corresponding to event onset, stop, and location.
- Whether or not the event was unexpected or unanticipated.
- Whether or not the event placed participants or others at greater risk of harm than was previously recognized.
- The degree to which the event was related to study procedures.
- Whether or not the study procedures were discontinued due to the event.
- The steps taken to remedy the event.
- The steps taken to report the event to the appropriate entities.
- (AE/SAE only) A ranking of the severity of the event according to section F2c.
- (AE/SAE only) The specific outcome of the event.
- (SAE only) The category of the SAE.

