Study staff will also generate an Annual Report during the last quarter of the year that will include a list and summary of any protocol deviation or violation that warrants a note-to-file, and AEs, SAEs, and unanticipated problems. In addition, the Annual Report will address (1) whether AE rates are consistent with pre-study assumptions; (2) reason for dropouts from the study; (3) whether all participants met entry criteria; (4) whether continuation of the study is justified on the basis that additional data are needed to accomplish the stated aims of the study; and (5) conditions whereby the study might be terminated prematurely. The Annual Report will be sent to all members of the DSMC. The DSMC along with the co-PIs will convene to review and discuss the report. The annual progress report will be forwarded to (1) the UW IRB and (2) NCCIH.

Study Report Outline for the Independent Monitor(s) (Interim or Annual Reports)

The study team will generate progress reports on a quarterly basis (three per year) for review by the Chair of the DSMC, as well as an annual report (during the final quarter of the year) to be reviewed by all DSMC members.

Study Report Outline

- I. Table of Contents
- II. Introduction
 - a. Summary of Study Status and Issues or Problems
- III. Study Administration
 - a. Recruitment Status
 - i. Overall Recruitment Status and Recruitment Source
 - ii. Comparison of Targeted to Actual Enrollment
 - iii. Reasons for Ineligibility
 - iv. Reasons for Declination, Unable to Contact, Deferral
- IV. Study Data Reports/Tables or Figures
 - a. General Information
 - i. Enrollment Status
 - ii. Demographic/Baseline Data
 - iii. Assessment Retention
 - iv. Treatment Participation
 - v. Treatment Fidelity
- V. Safety Assessment
 - a. SAEs
 - b. Adverse Events
 - c. Reportable Problems
 - d. Protocol Deviations

Study Report tables will be generated only from aggregate (not by group assignment) baseline and aggregate safety data for the study population.

F5. Reporting Changes in Study Status

During the funding of this study, any action by the IRB, the DSMC, or one of the study investigators that results in a temporary or permanent suspension of the study will be reported to the NCCIH Program Officer within 1 business day of notification.

G. Potential Benefits of Research to Participants and Others

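### The AE recording rule keeps only new, treated events, so non-serious worsening of an existing condition and untreated mild events are left out of the AE counts, although other safety sections describe wider capture

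*Combined protocol and SAP*

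**What the plan says.** F1a opens with a wide definition: "An adverse event (AE) is any untoward medical occurrence in a participant during participation in the clinical study". It goes on to include signs, symptoms and abnormal assessments, whatever their relation to the study. Its last sentence narrows what staff write down. The occurrence must meet the definition and must also be one that "is a new symptom/condition for the participant, and results in either self-treatment or treatment by a health care provider".

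F2c grades AEs from mild to life-threatening. The lowest grade reads "Mild: no intervention required; no impact on activities of daily living (ADL"). The next reads "Moderate: minimal, local, or non-invasive intervention indicated; moderate impact on ADL".

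F3a describes documentation without repeating the filter: "All regulatory events, incidents, or problems involving risks to participants, including AEs, SAEs, and Unanticipated Problems (UP), will be documented" in REDCap, with a form completed for each such event. F4g has staff and clinicians gather unsolicited reports, among them physical or psychological decline, but sends only AEs to the Regulatory Event form. It also says that charts will not be monitored for AEs.

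E3a, on reactions to assessments, warns that "some participants may focus more on their pain, which may lead to a temporary increase in pain intensity". F4g requires the annual report to the monitoring committee (DSMC) to address "whether AE rates are consistent with pre-study assumptions".

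**The concern.** The definition, the recording rule and the grading scale should cover the same events, and here they do not. The three conditions in F1a are joined by *and*, so failing any one keeps an occurrence off the AE form.

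The novelty condition matters most in this population. Under D5 every participant has had a chronic pain problem for at least 3 months, with average intensity of at least 3 on a 10-point scale. Worsening of that pain is a change in an existing condition, and F1a has no clause for worsening. The treatment condition removes a second group: new events too mild for anyone to treat.

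What is at stake is the meaning of the safety counts. AEs are summarised quarterly under F3b, and the F4g progress and annual reports carry them to the DSMC Chair and then the full committee. The Chair may consult the other members if AE rates look higher than expected, and the first stopping criterion in F4e concerns adverse effects of an intervention. A reader of those counts would not know that they omit worsening of existing conditions and untreated events.

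**Working it through.** No arithmetic applies: the documents give no observed, expected or assumed AE rate. The check is to run each type of event through F1a and compare the result with the other sections.

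| Event | New? | Treated? | Recorded as an AE under F1a? | What other sections imply |
|---|---|---|---|---|
| New, mild, untreated | yes | no | no | F2c has a grade for it |
| New, mild, self-treated though treatment was not required | yes | yes | yes | consistent with F2c grade 1 |
| New, moderate or worse, treated | yes | yes | yes | consistent |
| Existing condition worsens, non-serious, untreated | no | no | no | F4g collects reports of decline |
| Existing condition worsens, non-serious, treated | no | yes | no | F2c can grade it; seeking medical attention is a feature of grade 3 |
| Worsening that meets SAE or unanticipated-problem criteria | no | either | not needed | F1b, F1c and F3c give a separate route |

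**Does F3a or F4g override F1a?** F3a says AEs are documented, and F4g says AEs heard in sessions or elsewhere are recorded. Both use the term AE, and F1a is the only place that tells staff which occurrences to document. If F3a means AEs in the broad sense, it conflicts with the F1a filter. If it means AEs after the filter, it adds nothing. Neither section states which.

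**Do the separate routes cover the gap?** F1c (SAE) and F1b (unanticipated problem) do not repeat the filter, so serious worsening is reportable. F1b requires an event to be unexpected, at least possibly related, and suggestive of greater risk than was known. A temporary pain increase is already listed in E3a, so it would ordinarily not be unexpected. Non-serious, foreseen worsening thus has no route.

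**Is there another source?** Pain intensity and interference are rated twice daily by EMA through baseline, treatment and four weeks after treatment (D6j), and again at the extended assessments (Table 4). These are outcome data. F4g states that study report tables come only from aggregate baseline and aggregate safety data, and its report outline lists no EMA pain ratings. Worsening seen there is not planned to reach the DSMC as a safety signal.

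**The case against.** The best defence is that F1a sets a deliberate threshold for a low-risk behavioural trial. Pain fluctuates daily in these participants, and a form for every untreated fluctuation would bury the informative events. A definition followed by a narrower recording threshold is a mismatch of scope and need not be a logical contradiction. Much of this stands: recording every fluctuation is not clearly desirable. But the protocol gives no such rationale, does not say that reported rates are restricted in this way, and the threshold also drops worsening that was treated.

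Four stronger readings are tempting, and the documents do not support them.

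- *Grade 1 events can never be recorded.* F2c asks whether intervention was required; F1a asks whether treatment resulted. A new mild symptom that the participant chose to self-treat meets both.
- *Worsening pain cannot be recorded for anyone.* Serious worsening and unanticipated problems have their own routes, and pain is measured repeatedly as an outcome. The gap is non-serious worsening as an AE.
- *The most plausible harm of the interventions is excluded.* The pain increase is listed in E3a, on assessments. E3a does tie such self-monitoring effects to the treatment approaches, but no section ranks harms. E3b lists other harms, such as distress, grogginess and strain or injury in the activation skills arm. A strain would normally be new and, if treated, recorded.
- *The annual check of AE rates is uninformative.* No assumed rate is stated, nor the rule behind it. If the assumptions used the same restriction, the comparison keeps some meaning.

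**Conclusion.** Wrong as written. Under F1a, non-serious worsening of a pre-existing condition and untreated new mild events are not recorded as AEs. F2c grades such events, and F3a and F4g describe wider capture without clearly overriding the filter. The AE counts in the quarterly and annual reports therefore cover new, treated events only.

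The conclusion assumes that staff apply F1a literally and treat a flare of existing chronic pain as not new. A flare with a distinct new symptom could qualify if it was treated. How many events are lost cannot be estimated from the documents. The effect is confined to AE reporting: SAE and unanticipated-problem reporting, the primary mechanism analysis and the sample size are not touched.

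**What to change.** Reconcile F1a with F2c, F3a and F4g so that the recording rule, the grading scale and the collection plan describe the same events:

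- Extend the F1a documentation rule to clinically notable worsening of a pre-existing condition, whether or not treated, and to reported mild events that meet the AE definition. Say how notable worsening is judged, so that ordinary daily fluctuation does not generate forms.
- Hold new/worsened and treated/untreated as fields on the existing Regulatory Event form. The fields listed in F3a include steps taken to remedy the event, but none separates a new condition from a worsened one.
- State in F3a and F4g that AE there has the revised F1a meaning.
- If the treatment threshold is kept on purpose, say so, and label reported AE rates as treated events only in the DSMC reports and publications.

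The cost is protocol wording, one or two form fields and some additional event forms. No new visits, assessments or procedures are needed.

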Study researchers, including staff members and study clinicians who conduct the telephone assessments and facilitate the treatment groups, will collect safety information on an ongoing basis. By systematically monitoring for events, we will ensure that problems are detected immediately and addressed as indicated.

Treatment

Study clinicians will collect unsolicited information reported by participants during treatment sessions including, but not limited to, physical or psychological decline, or unexpected reactions to the treatment intervention.

Any AEs collected during treatment sessions will be recorded on the participant's REDCap Regulatory Events form created and completed during participation.

General

Research staff and study clinicians will collect unsolicited information reported by participants during study participation including suicidal thoughts or suicidal ideation (SI), increased alcohol/drug use, intentions to harm someone else, or psychological decline.

Any AEs collected during the course of the study will be recorded on the participant's REDCap Regulatory Events form created and completed during participation.

All information leading to an adverse event (AE), serious adverse event (SAE), or unanticipated problem (UP) will be reported per UW protocol/requirement, i.e., to UW IRB using the approved UW IRB forms. All documentation collected, submitted, and approved will be stored in a regulatory e-binder located within a limited access folder on the study server. We do not plan to monitor charts for AEs.

Safety information collection will begin as soon as study recruitment begins. Safety information collection will end once the participant completes the final assessment, i.e., approximately six months following completion of the intervention.

Progress Report (Quarterly)

Research staff will generate three quarterly study reports per year that outlines study progress including recruitment, retention/attrition, any protocol deviation or violation that warrants a note-to-file, and AEs, SAEs, and unanticipated problems for that particular quarter. This report will be provided to the Co-PIs and the Chair of the DSMC. The Chair of the DSMC may solicit input from the other DSMC members if she detects anything of concern (e.g., higher rates of AEs than anticipated). The Chair of the DSMC will generate a report if there is anything of concern that will be supplied to the study PIs, the UW IRB, and NCCIH.

Annual Report

Study staff will also generate an Annual Report during the last quarter of the year that will include a list and summary of any protocol deviation or violation that warrants a note-to-file, and AEs, SAEs, and unanticipated problems. In addition, the Annual Report will address (1) whether AE rates are consistent with pre-study assumptions; (2) reason for dropouts from the study; (3) whether all participants met entry criteria; (4) whether continuation of the study is justified on the basis that additional data are needed to accomplish the stated aims of the study; and (5) conditions whereby the study might be terminated prematurely. The Annual Report will be sent to all members of the DSMC. The DSMC along with the co-PIs will convene to review and discuss the report. The annual progress report will be forwarded to (1) the UW IRB and (2) NCCIH.

Study Report Outline for the Independent Monitor(s) (Interim or Annual Reports)

The study team will generate progress reports on a quarterly basis (three per year) for review by the Chair of the DSMC, as well as an annual report (during the final quarter of the year) to be reviewed by all DSMC members.

Study Report Outline

- I. Table of Contents
- II. Introduction
 - a. Summary of Study Status and Issues or Problems
- III. Study Administration
 - a. Recruitment Status
 - i. Overall Recruitment Status and Recruitment Source
 - ii. Comparison of Targeted to Actual Enrollment
 - iii. Reasons for Ineligibility
 - iv. Reasons for Declination, Unable to Contact, Deferral
- IV. Study Data Reports/Tables or Figures
 - a. General Information
 - i. Enrollment Status
 - ii. Demographic/Baseline Data
 - iii. Assessment Retention
 - iv. Treatment Participation
 - v. Treatment Fidelity
- V. Safety Assessment
 - a. SAEs
 - b. Adverse Events
 - c. Reportable Problems
 - d. Protocol Deviations

Study Report tables will be generated only from aggregate (not by group assignment) baseline and aggregate safety data for the study population.

F5. Reporting Changes in Study Status

During the funding of this study, any action by the IRB, the DSMC, or one of the study investigators that results in a temporary or permanent suspension of the study will be reported to the NCCIH Program Officer within 1 business day of notification.

G. Potential Benefits of Research to Participants and Others

Previous studies with the therapeutic skills taught in the planned study support their efficacy in reducing pain interference and improving other pain-related outcomes. We anticipate based on this previous research that many of the participants will experience significant reductions in their daily pain interference and other benefits associated with the treatments. Participants in all three conditions will have the benefit of a caring and interested group leader, thus promoting therapeutic alliance, as well as interaction with other group members.

In our past research, many group members have expressed satisfaction from learning that there are other people with experiences similar to their own, and from receiving group treatment in a caring and nonjudgmental environment. Thus, participants in all three treatments will take away from the study new skills and knowledge regarding chronic pain and how to manage it, and – given previous results of RCTs for psychosocial interventions for chronic pain – should experience some degree of relief from pain and suffering and increases in their quality of life.

H. Publication of Research Findings

Any manuscript will be made available for review by the study sponsor prior to submission.

I. Importance of Knowledge to Be Gained

The findings from this study will provide clinically meaningful information that will have positive effects on the lives of patients with chronic pain who endorse low back pain as a primary or secondary pain problem. The findings will provide important new information regarding mechanisms of the treatments studied, as well as those factors that underlie post-treatment relapse, maintenance, and continued gains following treatment. Results will elucidate the temporal sequence of lagged mechanism effects to determine rates of change in outcome as a function of change in cognitive content, cognitive process, and behavioral activity level. Results will also precisely inform relapse prevention interventions. As pointed out by Kazdin,^{12,13} progress in our understanding of treatments has been hampered by the lack of mechanism studies, such as the one planned, to identify the mechanisms of treatment outcome and relapse. The current study will help address this significant gap. The exploratory moderation findings will inform the future development of patient-treatment matching algorithms.

References

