The assessment period described above will be completed prior to initiating treatment, post-treatment (after session #8), and 3 and 6 months following the end of treatment for a total of four times. These assessment periods that occur following the start of treatment will also include questions about amount of time spent practicing skills learned in treatment, treatment satisfaction and treatment modality, and overall improvement since the participant began the treatment program. The assessments done at 3 and 6 months following the end of treatment

may be completed online by the participant via REDCap instead of verbally over the telephone with research staff. Regardless of modality, the items on both the online and verbally administrated versions of the extended assessments will be the same.

The participant will also be asked additional questions at post-treatment about their experiences in the group, as well as any feedback about the treatment program. Effective 2020, there will also be a question on COVID-19's impact during treatment. These questions will be collected by an unblinded staff member and should take approximately 15-30 minutes to complete. We will audio record and code up to 100 of these interviews until we reach saturation of themes. The audio recordings will not be labeled with any identifying information. The only identifying information that will be contained within the recordings will be participants' voices and if the staff member states a participant's name during the interview.

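### Adverse events are collected only passively: no standard question is named at any stage, and online follow-up can leave about half to 70% of the safety window without live contact

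*Combined protocol and SAP*

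**What the plan says.** F4g sets the standard: "By systematically monitoring for events, we will ensure that problems are detected immediately and addressed as indicated". It also sets the window. "Safety information collection will begin as soon as study recruitment begins", and "Safety information collection will end once the participant completes the final assessment, i.e., approximately six months following completion of the intervention".

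The method is described twice, and both descriptions are passive. Under Treatment: "Study clinicians will collect unsolicited information reported by participants during treatment sessions including, but not limited to, physical or psychological decline". Under General: "Research staff and study clinicians will collect unsolicited information reported by participants during study participation including suicidal thoughts or suicidal ideation (SI", with further examples of alcohol or drug use, intent to harm others and psychological decline. F4g adds: "We do not plan to monitor charts for AEs".

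The Appendix (Evaluation Timeline) marks Adverse Events in all nine columns, including the 3- and 6-month follow-ups. It names no instrument. D6g says that the assessments at those two times "may be completed online by the participant via REDCap instead of verbally over the telephone with research staff", with the same items in either mode. Table 2 likewise allows online or telephone.

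On expected harms, E3b says of the activation skills arm that "there is a risk that participants may experience physical strain or injury when conducting activities with a physical component", and E3c names skin irritation from the activity monitor.

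**The concern.** Systematic detection and unsolicited reporting are different things. If nobody asks, an event enters the record only when the participant thinks to mention it and has someone to mention it to. F1a has staff document a new condition that was self-treated or treated by a provider, and staff can seldom know that without asking.

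Several safeguards depend on the resulting counts. F4b has serious events reviewed as they occur, which presupposes that they are found. The first stopping rule in F4e turns on adverse effects of an intervention. The Annual Report in F4g checks event rates against what was assumed before the study. Hospital admissions are serious events under F1c, and one that occurs between the post-treatment call and month 6 could go unrecorded. The danger is that a small late count is then taken as reassurance.

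**Working it through.** **Is any question named?** The schedule and the listed content can be set side by side.

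- Appendix: Adverse Events due at all nine stages.
- Tables 1, 3 and 4: no adverse-event item at any time point.
- EMA content (D6j): pain, cognition, mood, self-efficacy, sleep and activity, with skills practice, alliance, group cohesion and treatment credibility at set times. No adverse-event item.
- Nearest item (Table 3): a one-item count of health-care visits over the last month. It records neither reason nor admission, and it covers about 1 of the 3 months between successive follow-ups.

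Events are therefore scheduled with no stated way of asking about them.

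**How long can a participant go without live contact?** Inputs:

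- pre-treatment assessment up to 7 weeks before treatment (D6g);
- baseline monitoring about 2 weeks and post-treatment monitoring 4 weeks (D6j);
- treatment about 4 weeks (D6m);
- post-treatment telephone assessment up to 2 months after treatment (Table 1);
- final assessment at about 6 months (F4g).

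One month = 365.25/12/7 = 4.35 weeks, so 6 months = 26.1 weeks and 2 months = 8.7 weeks.

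Check against the plan's own figure: 7 + 4 + 26.1 = 37.1 weeks, and 37.1/4.35 = 8.5 months. The Précis states 8 to 9 months, so it reproduces.

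Stretch after daily monitoring ends: 26.1 − 4 = 22.1 weeks. Stretch after a post-treatment call at its 2-month limit: 26.1 − 8.7 = 17.4 weeks.

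| Window counted from | Weeks to month 6 | After daily monitoring | After a call at 2 months |
|---|---|---|---|
| Session 1 | 4 + 26.1 = 30.1 | 22.1/30.1 = 73% | 17.4/30.1 = 58% |
| Start of baseline monitoring | 2 + 4 + 26.1 = 32.1 | 22.1/32.1 = 69% | 17.4/32.1 = 54% |
| Earliest pre-treatment assessment | 7 + 4 + 26.1 = 37.1 | 22.1/37.1 = 60% | 17.4/37.1 = 47% |

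The range is 47% to 73%. Counting from the end of monitoring is lenient to the plan: in those four weeks staff contact is prompted by missed diaries or non-wear, so a compliant participant may have none.

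Sensitivity: if the last assessment falls anywhere in its 5- to 8-month window (Table 1), the middle column runs from 54% to 79% and the last from 40% to 67%. With a 3-month lead-in (13.0 weeks, taking the D6c limit between enrolment and randomization as the lead-in), the window is 43.1 weeks and the shares are 22.1/43.1 = 51% and 17.4/43.1 = 40%.

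**The case against.** The strongest reply is that passive capture is still capture, and that it was a reviewed choice for interventions described as minimal risk. The revision history says that F4g was aligned with a monitoring plan the funder had approved. F1a defines an adverse event broadly. E4a offers every participant a discussion of adverse experiences with a co-PI, and E4b has supervisors routinely assess adverse events with clinicians. Staff follow up missed diaries and non-wear, send reminders before each follow-up, and can still do the assessments by telephone.

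Much of this stands, and it rules out some stronger readings.

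- **A reader might infer that most of the window has no working collection method, or that going online removed a question.** Neither is supported. Volunteered reporting runs throughout, and the items are the same in both modes. What online completion can remove is the conversation.
- **A reader might infer that physical injury outside sessions is excluded.** The General list is introduced by the word including, and F4g then provides for recording any adverse event. During treatment, an injury between sessions can be raised at the next one.
- **A reader might put the contact-free share at 26.1/32.1 = 81%.** That is an upper bound. It needs the call straight after Session 8, treats the four monitored weeks as contact-free, and starts the window after recruitment.
- **A reader might infer a false difference between arms,** since activation skills sessions and logs concern physical activity. That is possible, but any size put on it only returns the reporting rates assumed. No between-arm adverse-event analysis is specified, and the monitoring committee's tables are aggregate.

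The safeguards do not close the gap. The E4a offer concerns experiences tied to study procedures, whereas F1a counts events whatever their cause. Supervision questions clinicians, not participants. The plan describes the reminders only as prompts to complete the assessment.

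**Conclusion.** The point holds as a mismatch between promise and method, with a likely consequence. Ascertainment is passive from start to finish, while F4g promises systematic and immediate detection and the Appendix schedules adverse events at every stage. For a participant who does both follow-ups online, about 47% to 73% of the window need involve no live contact. Late events, including admissions, are then likely to be under-counted. The documents do not allow the size of the under-count to be estimated, and differential reporting by arm remains possible but unquantified.

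This rests on three assumptions: that the tables and D6g reflect the forms and scripts, which are not in the documents; that the participant chooses online completion twice; and that reminders are not live conversations. The point bears on safety reporting, not on the primary mechanism analysis.

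**What to change.** Reconcile F4g, Table 4 and the Appendix by naming one question, identical for all arms: any new or worsened health problem, injury, emergency visit or hospital admission since the last assessment, with its date.

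- Ask it at the post-treatment contact. The unblinded staff who conduct the qualitative interview are the natural people to ask. It should also reach participants who attended no session, who get no such interview under D6p.
- Put it on the 3- and 6-month forms in both online and telephone modes.
- Have existing staff review positive answers and enter them on the existing Regulatory Event form, using the version restricted to unblinded staff (F3a) where needed.
- Report solicited and volunteered events separately.

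The cost is one item on existing forms, an alert for positive answers and a short amendment. There will be more events to process, mostly minor, and counts before and after the change will not be comparable. Reach is limited: D2 ends enrolment at Month 06 of Year 05, about January 2022, before this version's date of March 15, 2022. Participants already past follow-up would not be covered, and reports should say that their late events were collected passively.
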